5.9 Duration of Follow Up

Patients will be followed for 1 year after removal from treatment or until disease progression, initiation of subsequent CLL therapy, or death, whichever occurs first. Patients removed from treatment for unacceptable adverse events will be followed until resolution or stabilization of the adverse event.

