6.3.5 Visit 6: 56 days after the last dose of DMF

6.3.5.1 Review concomitant medications

6.3.5.2 Physical exam including vital signs (temperature, pulse, respirations, blood pressure), weight; and including bidimensional measurement of palpable lymph nodes, spleen size (below the costal margin), and liver size (craniocaudal size at the right midclavicular line).

6.3.5.3 Performance status using ECOG grading scale.

6.3.5.4 Adverse event assessment: See Section 9 for adverse Event monitoring and reporting.

6.3.5.5 Hematology: hemoglobin (Hgb), platelets, total white blood cell count (WBC), and differential.

6.3.5.6 Serum chemistries: Comprehensive metabolic panel (CMP) to include: albumin, alkaline phosphatase, ALT/SGPT, AST/SGOT, BUN, creatinine,

electrolytes (sodium, potassium, calcium, chloride, bicarbonate), glucose, and total bilirubin.

6.3.5.7 Blood draw for correlative studies: Up to 20 mL in anticoagulated tubes.

6.3.6 Visits 7-10: Every 56 days to one year (typically month 6, 8, 10, 12)

Patients will be followed every 56 days after completion of (or early withdrawal from) study treatment until subsequent CLL therapy, death, or discontinuation of trial participation. Follow-up will consist of survival contacts via medical record review, telephone call, or review of the Social Security Index.

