6.5 Removal of Subjects from Study Treatment and Study

Patients can be taken off the study treatment and/or study at any time at their own request, or they may be withdrawn at the discretion of the investigator for safety, behavioral or administrative reasons. The reason(s) for discontinuation will be documented and may include:

6.5.1 Patient completed study treatment;

6.5.2 Patient voluntarily withdraws from treatment (follow-up permitted);

6.5.3 Patient withdraws consent (termination of treatment and follow-up);

6.5.4 Patient is unable to comply with protocol requirements;

- 6.5.5 Patient demonstrates disease progression (unless continued treatment with study drug is deemed appropriate at the discretion of the investigator);
- 6.5.6 Patient experiences toxicity that makes continuation in the protocol unsafe;
- 6.5.7 Treating physician judges continuation on the study would not be in the patient's best interest;
- 6.5.8 Patient becomes pregnant (pregnancy to be reported along same timelines as a serious adverse event);
- 6.5.9 Development of second malignancy (except for basal cell carcinoma or squamous cell carcinoma of the skin) that requires treatment, which would interfere with this study;
- 6.5.10 Lost to follow-up.

If a research subject cannot be located to document survival after a period of 2 years the subject may be considered "lost to follow-up." All attempts to contact the subject during the two years must be documented.

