10.4 Data Analyses Plans

Primary Analysis

The rate of DLTs will be estimated along with its exact 95% confidence interval using the patients treated at the selected dose in Phase I.

Secondary analyses

The adverse events from the treatment beginning to 56 days after treatment completion or study discontinuation will be recorded for all patients. Incidence of adverse events will be summarized by event type, grade and relatedness, separately for the two dose levels.

The proportion of patients that received the selected dose and are able to complete 2 months of therapy without intolerance or disease progression will be reported. The reason for patient discontinuing treatment early will be recorded.

The objective response rate (including partial response, complete response, or nodular complete response) based on iwCLL will be estimated along with its exact 95% confidence interval.

If follow-up is available, median progression-free survival and overall survival will be estimated using the Kaplan-Meier method.

The expressions of LEF1, c-myc, Wnt pathway, STAT pathway, and STAT1 phosphorylation will be measured over time. The trajectories will be showed by graphs. We will test if the average level of these measurements throughout the treatment is significantly changed from the pre-treatment level by a paired t-test at 5% significance level. We will use the methods of Smyth (2005) to fit linear models to assess differential expression between pre- and post-treatment measurements. As we plan to conduct a large number of hypothesis tests within the gene expression outcome, we will use the Benjamini-Hochberg method to control the false discovery rate (FDR), setting it to 5%.

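### Section 10.4 plans a Kaplan-Meier estimate of overall survival, but the two follow-up rules conflict and both can stop before death, which biases the curve upward if death risk rises after progression (minor)

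*Combined protocol and SAP*

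**What the plan says.** The analysis, in 10.4, is conditional on follow-up being available: "median progression-free survival and overall survival will be estimated using the Kaplan-Meier method". Sections 3.2 and 10.1 list progression-free survival (PFS) as a secondary endpoint. Neither lists OS, and no section says when a patient is censored for OS.

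Follow-up is described in three places:

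- Section 5.9: "Patients will be followed for 1 year after removal from treatment or until disease progression, initiation of subsequent CLL therapy, or death, whichever occurs first".
- Section 6.3.6 has contacts every 56 days "until subsequent CLL therapy, death, or discontinuation of trial participation". Progression is not in that list. On content it says: "Follow-up will consist of survival contacts via medical record review, telephone call, or review of the Social Security Index". Its heading places these visits at "Every 56 days to one year (typically month 6, 8, 10, 12").
- Section 6.5 sets a long search before a subject counts as lost: "If a research subject cannot be located to document survival after a period of 2 years", with all attempts documented.

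**The concern.** Kaplan-Meier is valid when patients censored at a given time have the same later death risk as those still followed. A patient whose follow-up ends because the leukemia has progressed, or because new treatment has started, is unlikely to meet that condition. If these patients go on to die sooner, their deaths are left out and the curve sits too high.

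The two sections also tell the site different things about a patient who has progressed but has not started new therapy: 5.9 ends follow-up and 6.3.6 continues it. The OS estimate therefore depends on which section the site follows.

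What is at stake is a published survival figure in a relapsed or refractory population that could look better than the truth. No dose decision, test or sample size rests on it.

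**Working it through.** **1. The rules side by side.**

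| Event | 5.9 | 6.3.6 |
|---|---|---|
| Progression, no new therapy | stop | continue |
| Next CLL therapy | stop | stop |
| Time limit | 1 year off treatment | one year, last visit about month 12 |

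With 56 days of treatment, the 5.9 limit is 56 + 365 = 421 days from start, or 13.8 months. The plan states no survival figure or event rate, so there is nothing of its own to reproduce and the size has to rest on assumptions.

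**2. Assumptions (none from the documents).** Exponential times. Median time to progression 3, 6 or 12 months (rate a). Median time to death without progression 60 months (rate b). Median survival after progression 6, 12 or 24 months (rate c). Median time from progression to next therapy 2 months (rate n), with death risk unchanged by that therapy. Each rate is ln 2 divided by its median. Put s = a + b.

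**3. Formulas.**

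- True OS: S(t) = exp(−st) + [a/(s − c)] × [exp(−ct) − exp(−st)].
- Kaplan-Meier under 5.9 (censored at progression): only deaths without progression count, so it tends to exp(−bt).
- Kaplan-Meier under 6.3.6 (censored at next therapy): exp of minus the integral of h(t) = (b·P0 + c·P1)/(P0 + P1). Here P0 = exp(−st), P1 = [a/(s − q)] × [exp(−qt) − exp(−st)] and q = c + n.

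**4. One case in full** (medians 6, 60 and 12 months). a = 0.1155, b = 0.01155, c = 0.05776, s = 0.1271 per month. At 12 months exp(−st) = 0.2176 and exp(−ct) = 0.5, so

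S(12) = 0.2176 + (0.1155/0.0693) × (0.5 − 0.2176) = 0.688.

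Under 5.9 the curve reads exp(−0.01155 × 12) = 0.871. Under 6.3.6 it reads 0.77. Of the deaths up to day 421, about 20% are seen under 5.9 and 47% under 6.3.6.

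**5. All nine cases, 12-month OS in percent** (bias in points, from the rounded figures).

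| Median to progression | Median survival after | True | 5.9 (bias) | 6.3.6 (bias) |
|---|---|---|---|---|
| 3 | 6 | 41 | 87 (+46) | 54 (+13) |
| 3 | 12 | 61 | 87 (+26) | 69 (+8) |
| 3 | 24 | 76 | 87 (+11) | 79 (+3) |
| 6 | 6 | 54 | 87 (+33) | 68 (+14) |
| 6 | 12 | 69 | 87 (+18) | 77 (+8) |
| 6 | 24 | 79 | 87 (+8) | 83 (+4) |
| 12 | 6 | 67 | 87 (+20) | 77 (+10) |
| 12 | 12 | 76 | 87 (+11) | 82 (+6) |
| 12 | 24 | 82 | 87 (+5) | 85 (+3) |

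Simulation of 300,000 patients per case agrees to within rounding. Deaths seen by day 421 run from 7% to 50% under 5.9 and from 38% to 66% under 6.3.6.

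**6. Equal risk.** If c = b, the true curve is also exp(−bt), and neither rule biases it. Some deaths are still missed, which costs precision only.

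**7. The planned median.** Under 5.9 the expected curve at 13.8 months is still exp(−0.01155 × 13.8) = 0.85. In the first row the true median falls before 12 months (true OS 41%), yet 5.9 reads 87% and 6.3.6 reads 54% at that time.

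**The case against.** The strongest reply has four parts.

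- **The two sections can be read as complementary:** clinical follow-up in 5.9, survival contacts in 6.3.6, supported by the two-year search in 6.5. That is a sensible reading, but the documents do not state it, and survival contacts would still end at next CLL therapy.
- **The analysis is conditional on follow-up being available.** True, but follow-up would be cut by a rule tied to the course of the disease. What is available is then a selected part, and the wording does not repair that.
- **The size is assumed.** This stands. The constant 87% under 5.9 only restates the assumed rate of death without progression; it is not a prediction. With equal death risk before and after progression there is no bias, and if the next therapy lowered the death risk, the bias from stopping there could shrink or reverse.
- **OS is not a listed endpoint, and a median would often be reported as not reached from 15 to 21 patients.** This stands too, and it sets the low severity.

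Three stronger readings are not supported. A reader might infer that most deaths will go unseen; that depends on unstated rates and does not hold generally under 6.3.6. A reader might infer that PFS is equally damaged; stopping at progression does not harm PFS, though stopping at next therapy before progression can.

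A reader might also infer that the 2-year study duration in the summary cannot hold the follow-up. With three dose levels, as in the summary, 15 patients need five successive 56-day windows: 5 × 56 + 365 = 645 days, inside 730, though at about 3.6 patients a month or faster once accrual gaps are counted. Only the 21-patient path, with seven windows and a full year after treatment, exceeds 730 whatever the accrual: 7 × 56 + 365 = 757, by 27 days. The documents give no accrual rate, do not define the 2 years, and set no data cut there.

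**Conclusion.** The point holds, as a minor one. Sections 5.9 and 6.3.6 disagree on whether follow-up goes on after progression, both end it at next CLL therapy, and 10.4 has no OS censoring rule. Applied as written, either rule censors patients at a point linked to their prognosis. The direction is upward if death risk is higher after progression; the documents do not establish that it is, but in this population it is the case to plan for. The ranges in the working (5 to 46 points under 5.9, 3 to 14 under 6.3.6) illustrate how far the choice of rule matters and are not forecasts. The MTD, the DLT rate and the response rate are untouched.

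**What to change.** Choose one of two.

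1. Delete OS from 10.4. This costs nothing, since OS is not an endpoint.
2. Keep OS and make follow-up support it. Reconcile 5.9 with 6.3.6 so that record review, telephone contact and death-index review continue for every patient to one fixed time, for example 1 year after treatment, regardless of progression or next CLL therapy. State in 10.4 that OS runs from start of treatment to death from any cause, censored only at the date last known alive or at that fixed time. Align the visit calendar in 6.3.6 (about month 12) with the same limit (about month 14 if it is 1 year after treatment).

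Under option 2 the 12-month Kaplan-Meier estimate matches the true value in the calculation above, provided vital status is obtained. The cost is a protocol amendment and a few extra contacts or record checks per patient, by means that 6.3.6 already lists.

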11.0 STUDY MANAGEMENT

11.1 Conflict of Interest

Any investigator who has a conflict of interest with this study (patent ownership, royalties, or financial gain greater than the minimum allowable by their institution, etc.) must have the conflict reviewed according to UCSD conflict of interest policy.

11.2 Institutional Review Board (IRB) Approval and Consent

The IRB should approve the consent form and protocol prior to any study-related activities. It is expected that the IRB will have the proper representation and function in accordance with federally mandated regulations.

In obtaining and documenting informed consent, the investigator should comply with the applicable regulatory requirement(s), and should adhere to Good Clinical Practice (GCP) and to ethical principles that have their origin in the Declaration of Helsinki.

Before recruitment and enrollment onto this study, the patient will be given a full explanation of the study and will be given the opportunity to review the consent form. Each consent form must include all the relevant elements currently required by the FDA Regulations and local or state regulations. Once this essential information has been provided to the patient and the investigator is assured that the patient understands the implications of participating in the study, the patient will be asked to give consent to participate in the study by signing an IRB-approved consent form.

Prior to a patient's participation in the trial, the written informed consent form should be signed and personally dated by the patient and by the person who conducted the informed consent discussion.

11.3 Subject Data Protection

In accordance with the Health Information Portability and Accountability Act (HIPAA), subjects who have provided written informed consent must also sign a subject authorization to release medical information to the study Sponsor and allow a regulatory authority, or Institutional Review Board access to subject's medical information relevant to the study.

11.4 Data and Safety Monitoring/Auditing

In addition to adverse event monitoring and clinical oversight by the principal investigator and co-investigators, quality assurance of the study will be performed by the clinical trials office

internal monitor. Monitoring intervals will be dependent upon the number of patients enrolled and the complexity of the study.

This study will also use the UCSD Moores Cancer Center Data Safety and Monitoring Board (DSMB) to provide oversight in the event that this treatment approach leads to unforeseen toxicities. Data from this study will be reported after every 6 patients or sooner if required for clinical study stopping rules, and will include:

- 1) the protocol title, IRB protocol number, and the activation date of the study.
- 2) the number of patients enrolled to date
- 3) the date of first and most recent patient enrollment
- 4) a summary of all adverse events regardless of grade and attribution
- 5) a response evaluation for evaluable patients when available
- 6) a summary of any recent literature that may affect the ethics of the study.

11.5 Adherence to the Protocol

Except for an emergency situation in which proper care for the protection, safety, and well-being of the study patient requires alternative treatment, the study shall be conducted exactly as described in the approved protocol.

11.5.1 Emergency Modifications

Investigators may implement a deviation from, or a change of, the protocol to eliminate an immediate hazard(s) to trial subjects without prior IRB approval.

For any such emergency modification implemented, a IRB modification form must be completed within five (5) business days of making the change.

11.5.2 Other Protocol Deviations/Violations

All other planned deviations from the protocol must have prior approval by the Principal Investigator and the IRB. According to the IRB, a protocol deviation is any unplanned variance from an IRB approved protocol that:

- Is generally noted or recognized after it occurs
- Has no substantive effect on the risks to research participants
- Has no substantive effect on the scientific integrity of the research plan or the value of the data collected
- Did not result from willful or knowing misconduct on the part of the investigator(s).

An unplanned protocol variance is considered a violation if the variance:

- Has harmed or increased the risk of harm to one or more research participants.
- Has damaged the scientific integrity of the data collected for the study.
- Results from willful or knowing misconduct on the part of the investigator(s).
- Demonstrates serious or continuing noncompliance with federal regulations, State laws, or University policies.

If a deviation or violation occurs without prior approval from the Principal Investigator, please follow the guidelines below:

Protocol Deviations: Personnel will report to any sponsor or data and safety monitoring committee in accordance with their policies. Deviations should be summarized and reported to the IRB at the time of continuing review.

Protocol Violations: Study personnel should report violations within one (1) week of the investigator becoming aware of the event using the same IRB online mechanism used to report Unanticipated Problems.

11.6 Amendments to the Protocol

Should amendments to the protocol be required, the amendments will be originated and documented by the Principal Investigator. It should also be noted that when an amendment to the protocol substantially alters the study design or the potential risk to the patient, a revised consent form might be required.

The written amendment, and if required the amended consent form, must be sent to the IRB for approval prior to implementation.

11.7 Record Retention

Study documentation includes all Case Report Forms, data correction forms or queries, source documents, Sponsor-Investigator correspondence, monitoring logs/letters, and regulatory documents (e.g., protocol and amendments, IRB correspondence and approval, signed patient consent forms).

Source documents include all recordings of observations or notations of clinical activities and all reports and records necessary for the evaluation and reconstruction of the clinical research study.

Government agency regulations and directives require that the study investigator must retain all study documentation pertaining to the conduct of a clinical trial. In the case of a study with a drug seeking regulatory approval and marketing, these documents shall be retained for at least two years after the last approval of marketing application in an International Conference on Harmonization (ICH) region. In all other cases, study documents should be kept on file until three years after the completion and final study report of this investigational study.

11.8 Obligations of Investigators

The Principal Investigator is responsible for the conduct of the clinical trial at the site in accordance with Title 21 of the Code of Federal Regulations and/or the Declaration of Helsinki. The Principal Investigator is responsible for personally overseeing the treatment of all study patients. The Principal Investigator must assure that all study site personnel, including sub-investigators and other study staff members, adhere to the study protocol and all FDA/GCP/NCI regulations and guidelines regarding clinical trials both during and after study completion.

The Principal Investigator at each institution or site will be responsible for assuring that all the required data will be collected and entered onto the Case Report Forms. Periodically, monitoring visits will be conducted and the Principal Investigator will provide access to his/her original records to permit verification of proper entry of data. At the completion of the study, all case report forms will be reviewed by the Principal Investigator and will require his/her final signature to verify the accuracy of the data.

Appendix A. Performance Status

ECOG Performance Status Scale	
Grade	Descriptions
0	Normal activity. Fully active, able to carry on all pre-disease performance without restriction.
1	Symptoms, but ambulatory. Restricted in physically strenuous activity, but ambulatory and able to carry out work of a light or sedentary nature (e.g., light housework, office work).
2	In bed < 50% of the time. Ambulatory and capable of all self-care, but unable to carry out any work activities. Up and about more than 50% of waking hours.
3	In bed > 50% of the time. Capable of only limited self-care, confined to bed or chair more than 50% of waking hours
4	100% bedridden. Completely disabled. Cannot carry on any self-care. Totally confined to bed or chair
5	Dead.

Appendix B. Hematologic AE grading scale

Taken from iwCLL guidelines, Hallek et al, 2008.

Table 5. Grading scale for hematologic toxicity in CLL studies

Grade*	Decrease in platelets† or Hb‡ (nadir) from pretreatment value, %	Absolute neutrophil count/μL§ (nadir)
0	No change to 10%	≥ 2000
1	11%-24%	≥ 1500 and < 2000
2	25%-49%	≥ 1000 and < 1500
3	50%-74%	≥ 500 and < 1000
4	≥ 75%	< 500

*Grades: 1, mild; 2, moderate; 3, severe; 4, life-threatening; 5, fatal. Death occurring as a result of toxicity at any level of decrease from pretreatment will be recorded as grade 5.

†Platelet counts must be below normal levels for grades 1 to 4. If, at any level of decrease, the platelet count is $< 20 \times 10^9/L$ ($20\,000/\mu L$), this will be considered grade 4 toxicity, unless a severe or life-threatening decrease in the initial platelet count (eg, $20 \times 10^9/L$ [$20\,000/\mu L$]) was present pretreatment, in which case the patient is not evaluable for toxicity referable to platelet counts.

‡Hb levels must be below normal levels for grades 1 to 4. Baseline and subsequent Hb determinations must be performed before any given transfusions. The use of erythropoietin is irrelevant for the grading of toxicity but should be documented.

§If the absolute neutrophil count (ANC) reaches $< 1 \times 10^9/L$ ($1000/\mu L$), it should be judged to be grade 3 toxicity. Other decreases in the white blood cell count, or in circulating neutrophils, are not to be considered because a decrease in the white blood cell count is a desired therapeutic endpoint. A gradual decrease in granulocytes is not a reliable index in CLL for stepwise grading of toxicity. If the ANC was $< 1 \times 10^9/L$ ($1000/\mu L$) before therapy, the patient is not evaluable for toxicity referable to the ANC. The use of growth factors such as G-CSF is not relevant to the grading of toxicity, but should be documented.
